Study Title: Topical bimatoprost for chemical blepharoplasty

1. Study aim, background, and design

Study aim:

Topical bimatoprost has been shown to cause periorbital changes of soft tissue which are most pronounced when used directly onto the cornea for the treatment of glaucoma. Changes are primarily felt to be the result of prostaglandin-mediated adipocyte loss, resulting in deepening of the upper eyelid sulcus and recession of infraorbital pseudoherniation. Use of topical bimatoprost to the upper eyelid margin, now FDA approved for eyelash enhancement, may provide a metered effect on the periocular tissues and allow for a topical approach to periocular rejuvenation. I propose a proof of concept, small scale study to identify change in dermatochalasis with use of bimatoprost along the lid margin.

Background:

Perception of beauty in the periocular region is influenced by several factors, including symmetry, population norms, and skin texture and tone. Soft tissue and skin changes over time create an aged appearance with the development of dermatochalasis, blepharoptosis, lacrimal gland prolapse, and fat prolapse¹. Techniques for periocular rejuvenation are well established and include soft tissue augmentation, resurfacing, and surgical correction. In May 2015, Sarnoff and Gotkin reported a case of "chemical blepharoplasty" achieved with topical bimatoprost ophthalmic 0.03% solution applied to the upper eyelid margin. After three months of use, the author noted a more youthful appearance of the periocular region, with deepening of the upper eyelid sulcus, reduction in dermatochalasis, and diminution of the inferior eyelid fat pad. These changes were attributed to the prostaglandin associated periorbitopathy (PAP), a well described phenomenon observed with the use of topical prostaglandin analogues use for glaucoma.

Periorbital changes observed with topical prostaglandin analogues are primarily due to effects on aponeurotic and deep orbital adipocytes³. Prostaglandins activate the adipocyte MAPK pathway, leading to inactivation of PPAR-gamma, inhibition of adipocyte differentiation, and decreased fat accumulation within adipocytes^{1,4}. Bimatoprost concentration-dependent contractions of ciliary muscles and activation of matrix metalloproteinases³ may also contribute to periocular changes. Patients using topical ophthalmic prostaglandin analogues commonly develop periorbital fat loss, which has been well characterized in the ophthalmology literature.

Bimatoprost applied to the upper eyelid margin for eyelash enhancement attempts to capitalize on the desirable effects of darker, longer, thicker eyelashes, while limiting more significant and undesirable effects through limited exposure of the drug to ocular tissues. This same concept

Version Date: 07/26/16 Version Number: 2

Page 1 of 5

may apply for dermatochalasis: at a metered dose, topical bimatoprost to the lid margin could lead to subtle periorbital fat loss resulting in improved dermatochalasis.

Study design:

This is a proof of concept study which aims to enroll a series of patients with mild to severe dermatochalasis, treat with topical bimatoprost 0.03% solution to the upper lid margin, and evaluate for cosmetic improvement of the periocular area.

15 subjects will be recruited.

2. Subject Population

Inclusion criteria: 18+, mild to severe dermatochalasis, desire for enhanced eyelashes

Exclusion Criteria: Patients with current use of ophthalmic prostaglandin analogues, history of blepharoplasty, history of neuromodulators or fillers to the periocular region or frontalis in the last 6 months, existing deep upper eyelid sulcus, opposition to eyelash enhancement, pregnancy (This small proof of concept series aims to look at a new use of an already FDA approved medication. Currently this medication is pregnancy category C and has not been studied in children. As such we will only expose the patient population in which this medication has been determined to be safe.)

Patients will be recruited through our medical dermatology and cosmetic dermatology clinics at our University by faculty and residents based on inclusion criteria.

Recruiting script:

"I am doing a study looking at the use of the medication Latisse, which is currently FDA approved for eyelash enhancement, for possible effects it could have on drooping eyelids, or dermatochalasis. Involvement in the study would involve use of the product nightly as well as monthly visits for 4 months. Would you be interested in getting more information on this study?"

3. Procedure

At the initial visit, the study as well as known benefits and side effects of topical bimatoprost will be discussed with the patient. Written informed consent will be obtained for study inclusion, treatment, and photographic documentation. An initial examination and photodocumentation will be performed, and application instructions per the package insert. ("...should be applied every night using only the accompanying sterile applicators. They should start by ensuring their face is clean, all makeup is removed, and their contact lenses removed (if applicable). Then, carefully place one drop of LATISSE® solution on the disposable sterile applicator and brush cautiously along the skin of the upper eyelid margin at the base of the eyelashes. If any

Version Date: 07/26/16 Version Number: 2 LATISSE® solution gets into the eye proper, it will not cause harm. The eye should not be rinsed.")

Potential side effects to be discussed include potential for itching sensation of the eyes or eyelids, intraocular pressure effects, eyelid skin redness or darkening, iris darkening, unexpected hair growth or eyelash changes. Patients will be informed to contact the primary study investigator with any acute ocular changes (trauma, infection), sudden decrease in visual acuity, or eyelid/eye irritation.

The patients will be asked to use the medication nightly, and will be followed with Q 4 weeks appointments for a total of 4 visits.

Data collection:

Demographic information will be collected on all patients, including: age, sex, ethnic background.

An entry survey will be completed requesting self evaluation of the periocular area. (Appendix A)

Patients will be followed Q 4 weeks in clinic with followup photodocumentation at each visit for a total of 4 visits, 3 months of treatment.

During each visit, application instructions will be reviewed to ensure appropriate use. Each patient will be asked to complete a survey inquiring about potential side effects to ensure continued safety at followup visits (**Appendix B**), as well as an exit survey (**Appendix C**)

At completion of the study period, each patient's photographs at weeks 0, 4, 8, and 12 will be graded by 2 blinded evaluators for level of dermatochalasis: -1 (deep upper eyelid sulcus), 0 (no dermatochalasis), 1 (mild, slightly noticeable), 2 (moderate, noticeable), or 3 (severe, distinctive). Grading will be assisted by a visual aid adapted from a scale published by Shah et al. **(Appendix D)**

4. Risks

The patients participating in the study are subject to minimal risk with use of the topical medication. If experienced, side effects such as eye or eyelid irritation, eyelid discoloration, and iris dyspigmentation will resolve with medication discontinuation. Patients may be referred to an appropriate physician specialist if needed. No direct psychological or social harm is expected.

Confidentiality of data will be maintained via a system of de-identification and password protection. First, each patient will be assigned a code (P1-15) by which they will be identified. The code key will be stored in a password protected excel document on the PI's computer. Demographic data as well as survey answers will be stored without patient names (only P#),

Version Date: 07/26/16 Version Number: 2 again in a password protected excel document.

At the cessation of the study the key will be destroyed, leaving only de-identified information.

Photographs will be taken on a digital memory card reserved only for use in the study. Photographs that include our study area, the eyes, are difficult to de-identify. Photos will include only the eyebrows and eyes in an effort to minimize face recognition. Patients will be asked to sign a separate photograph consent detailing this information.

All data is stored on a password protected laptop to which only the PI has access.

Combined, de-identified data and photographs will be used for medical education, presentations, and publication. This information is included in the consent forms.

5. Benefits

The medication is currently FDA approved for eyelash enhancement. patients can expect to see increased length and density of eyelashes.

Improvement in dermatochalasis may be seen.

6. Remuneration

There will be no payment for participation in this research study.

7. Academic or Extra Credit

NA

8. Costs

There will be no costs to the subject for participating in this research study.

9. Alternatives

The subjects do not have to participate in the research.

10. Consent process and documentation

Written informed consent will be obtained for study participation as well as medical photography.

11. Qualifications of the investigators

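### Only current prostaglandin-analogue use is excluded, so a recent user with a partial effect can enter and may bring a lowered week-0 grade

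*Protocol*

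**What the plan says.** The exclusion sentence in Protocol section 2 (Subject Population) handles earlier periocular treatment in three different ways. It opens "Patients with current use of ophthalmic prostaglandin analogues, history of blepharoplasty": the drug class counts only while it is being used, whereas eyelid surgery counts whenever it took place. It continues "history of neuromodulators or fillers to the periocular region or frontalis in the last 6 months", which is a dated look-back. It also lists "existing deep upper eyelid sulcus". Inclusion is "18+, mild to severe dermatochalasis, desire for enhanced eyelashes", and on the source of participants the section says "Patients will be recruited through our medical dermatology and cosmetic dermatology clinics". The target is 15 people.

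Section 3 (Procedure, Data collection) sets 4-weekly visits "for a total of 4 visits, 3 months of treatment". Two blinded evaluators grade the photographs from weeks 0, 4, 8 and 12 on a scale from -1 (deep sulcus) through 0 (none) to 3 (severe). No control group is described. Besides age, sex and ethnic background, the text names three forms. On the first it says "An entry survey will be completed requesting self evaluation of the periocular area"; the second is a "survey inquiring about potential side effects to ensure continued safety at followup visits"; the third is an exit survey. These are Appendices A to C, which are not shown.

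Section 1 gives periorbital fat loss as the expected mechanism, calls it common in users of ophthalmic prostaglandin analogues, and cites one case of reduced dermatochalasis after three months of lid-margin use. Section 4 (Risks) says that irritation, discoloration and iris changes resolve on stopping. It does not mention fat loss.

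**The concern.** The protocol accepts that recent periocular treatment can spoil the baseline, and it sets a time window for neuromodulators and fillers. For the class of drug under study it sets none, so on the wording a person who stopped last week is eligible.

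This matters because each person is his or her own comparator. A participant who has already had part of the effect, and still has it at entry, starts from a lower week-0 grade and may have less change left to show. In a proof-of-concept series the likely harm is a diluted signal. The exposure would also be hard to reconstruct later, since section 4 has the code key destroyed when the study ends.

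A lesser matter is that the neuromodulator and filler restriction is phrased as a history at selection. Nothing in the text shown carries it through week 12, and a treatment given in that time could alter the later photographs in either direction.

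**Working it through.** The plan gives no alpha, power, effect size or standard deviation for its 15 participants, so there is no stated figure to reproduce. The check is a reading of the eligibility rules, followed by a bounding calculation.

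**Step 1: who can enter.** Mild to severe dermatochalasis corresponds to grades 1, 2 and 3 on the section 3 scale. Suppose prior use lowered a person's grade by one step:

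| Before prior use | At entry | Eligible on severity? |
|---|---|---|
| 3 | 2 | yes |
| 2 | 1 | yes |
| 1 | 0 | no |

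The severity requirement and the deep-sulcus exclusion together remove a marked prior effect, but they let a partial one through. The table shows which steps are possible. It says nothing about how often they occur.

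**Step 2: effect on the baseline.** If k of the 15 enter with a grade lowered by one step, the mean week-0 grade falls by k/15:
- k = 1: 1/15 = 0.07 grade
- k = 3: 3/15 = 0.20 grade

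**Step 3: effect on the mean change.** Let D be the mean change that would be seen in people with no prior use. Assume that a past user's total response is fixed and that a share f of it is already present at week 0 and stays. That person then shows only (1 - f)D, and

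mean change = [(15 - k)D + k(1 - f)D] / 15 = D(1 - kf/15).

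| k (assumed) | f = 0 | f = 0.5 | f = 1 (worst case) |
|---|---|---|---|
| 1 | no loss | 3.3% loss | 1/15 = 6.7% loss |
| 3 | no loss | 10% loss | 3/15 = 20% loss |

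Both k and f are assumptions, and so is the fixed total response. The scale runs down to -1, so a person entering at grade 1 or 2 still has room to fall. If further treatment produces a further response, the loss is smaller than shown and may be nil.

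**Step 4: an effect that is wearing off.** The formula covers only a stable prior effect. If the effect was fading, the outcome depends on how much had gone by week 0 and how much goes afterwards. The documents give neither, so no direction can be assigned.

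**Step 5: treatments during follow-up.** A neuromodulator or filler given after week 0 is at most 12 weeks old at the last photograph, which lies inside the 6 months that the protocol treats as too recent at entry. This shows that the protocol's own standard would apply. It does not measure a bias.

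**The case against.** The strongest reply is that the main bias needs an effect that outlasts treatment, and the documents do not supply one. Section 1 offers mechanisms but no duration. A reader might infer persistence from section 4's silence on fat loss, but silence is not evidence either way. With f = 0 the dilution is nil. This stands, and the point has to remain conditional.

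It can also be said that wanting longer lashes and attending a cosmetic clinic fit a never-user just as well. That stands too: prior use is plausible here, but no rate is given. The present wording arguably already reaches current use of the lid-margin product, since section 1 describes that product as an ophthalmic solution. Granted; what stays open is the time window, and naming eyelash products only removes doubt.

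Different look-backs for different treatments do not conflict in themselves. A reader might call this a contradiction in the protocol, but it is a gap in a design choice.

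Three other strong readings are tempting. One is that the bias could hide an effect but never create one; that holds only for a stable persisting effect (Step 4). Another is that 7% or 20% is the loss to expect; these are ceilings under a fixed total response. The third is that procedures during the study go unrecorded; this cannot be shown, because Appendices A to C are not at hand and may ask about them.

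None of these replies closes the eligibility gap. Even forms that record prior use would not change who may enter. Nor can the matter be left to an analysis plan, because eligibility is fixed in the protocol and an exposure that was never collected cannot be adjusted for.

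**Conclusion.** The point holds as a design weakness of moderate weight. The exclusion stops at current use, the other entry criteria do not catch a partial prior effect, and there is no control group to absorb a shifted baseline. If the earlier effect persists, the measured change may be biased toward none.

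The size cannot be derived from the documents, which give no rate of prior use and no duration of effect after stopping. The only defensible figure is the upper limit of k/15 from Step 3, which requires a fixed total response already fully obtained. Confidence is medium: the wording is certain, its consequence is not.

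The entry-only wording of the neuromodulator and filler restriction is secondary and minor. It is a missing detail with unknown frequency and direction, and the forms may already deal with it.

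**What to change.** In section 2, replace current use with current or recent use of any prostaglandin analogue, and name eyelash products explicitly. The investigator should set the look-back and give the reason for its length. Record prior use, with the date of stopping, at entry.

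For the secondary point, unless the survey forms already do so, ask at each planned visit about any neuromodulator or filler treatment to the periocular region or frontalis, and date it, so that affected photographs can be identified.

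The cost is one change of wording, an entry item on prior use and, if the forms lack it, one question per planned visit. The downside is a slightly smaller recruitment pool.

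### Recent periocular resurfacing is neither excluded nor washed out, so an effect still evolving after week 0 could not be told apart from bimatoprost

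*Protocol*

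**What the plan says.** The Background (section 1) lists how the ageing eye area is usually treated: "Techniques for periocular rejuvenation are well established and include soft tissue augmentation, resurfacing, and surgical correction".

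Among the exclusions in section 2 (Subject Population) are "history of blepharoplasty, history of neuromodulators or fillers to the periocular region or frontalis in the last 6 months". Resurfacing is not among them. It does not return anywhere after the Background, whether as an exclusion, a washout or an item to record.

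The Study design paragraph describes one treated group. The study "aims to enroll a series of patients with mild to severe dermatochalasis, treat with topical bimatoprost 0.03% solution to the upper lid margin", and will then "evaluate for cosmetic improvement of the periocular area". The size is fixed without a derivation: "15 subjects will be recruited".

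The outcome under Data collection (section 3) is photographic: "photographs at weeks 0, 4, 8, and 12 will be graded by 2 blinded evaluators for level of dermatochalasis", on an integer scale from -1 to 3. The demographic items listed there are age, sex and ethnic background. Recruitment is partly from a cosmetic practice: "Patients will be recruited through our medical dermatology and cosmetic dermatology clinics at our University".

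**The concern.** The look-back for neuromodulators and fillers implies that the investigator regards recent cosmetic treatment of this area as a threat to reading the outcome. Resurfacing is a comparable treatment of the same area, and no reason is given for handling it differently. Under the rule as written, someone resurfaced a few weeks before entry may enrol and be photographed at week 0 while the result of that treatment may still be changing.

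Nothing else in the design protects against this. There is no control group in which the same drift would show. Blinding the two evaluators guards against expectation but cannot reveal why an eyelid looks different. If procedure history is not collected, no later analysis can separate such patients. Eligibility is also fixed at enrolment, so this is not something a statistical analysis plan could supply.

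**Working it through.** **Step 1: the named techniques against the entry rule.**

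| Technique | Named in Background (section 1) | Entry rule in section 2 |
|---|---|---|
| Soft tissue augmentation | yes | fillers, last 6 months |
| Resurfacing | yes | none |
| Surgical correction | yes | blepharoplasty, no time limit |
| Neuromodulators | no | last 6 months |

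Of the three classes named, resurfacing alone has no matching rule of any kind.

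**Step 2: when the gap causes bias.** Write a patient's change in grade from week 0 to week 12 as

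change = D + [R(12) − R(0)] + other causes,

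where D is the bimatoprost effect and R(t) is the contribution of earlier resurfacing to the grade at week t.

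- If the earlier effect is complete and stable at week 0, R(12) = R(0). The bracket is zero and there is no bias.
- If it is still evolving, R(12) differs from R(0). With one arm, D and the bracket are seen only as a sum. The sign of the bracket is not known from the documents: it could inflate or mask a drug effect.

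The point therefore concerns recent resurfacing only.

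**Step 3: scale.** The only usable input is the sample size of 15 (Study design). The weight of one patient is 1/15 = 0.067, or 6.7% of the sample. If the bracket moved one patient's grade by one level, the mean change would move by 1/15 = 0.067 grade. If it changed that patient's status from not improved to improved, the proportion improved would move by 6.7 percentage points. That proportion is used here for illustration; the protocol does not name it as an endpoint.

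The protocol gives no figure on this point to reproduce, and none for the number of recently resurfaced patients or the size or duration of their effect. The 6.7% is the weight of any patient for any cause, not an estimate of bias.

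**The case against.** The strongest reply is that the Background sentence is general context, not a list of confounders that the exclusions were meant to mirror. Neuromodulators are excluded although that sentence does not name them, so the exclusions were not built from it. That stands: this is a gap in the entry rule, not a self-contradiction.

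Second, nothing in the documents says that resurfacing alters the dermatochalasis grade, or that any such change continues after week 0. To matter, an effect must be still evolving and large enough to move a patient across an integer grade. This also stands, and it limits the point to a possibility.

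A reader might infer three stronger things that the documents do not support:

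- *That resurfacing carry-over would be credited to bimatoprost.* Size, direction and duration are not given, so it could be, no more.
- *That such patients are likely.* Patients are "recruited through our medical dermatology and cosmetic dermatology clinics", and no frequency of earlier resurfacing is given. A cosmetic clinic makes it plausible only.
- *That any earlier periocular or brow surgery should be barred, because surgical correction is named generally and only blepharoplasty is excluded.* A remote operation with a stable result is already in the baseline photograph, so an unlimited bar would cost candidates without reducing bias.

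It may also be said that the initial examination or the entry survey (Appendix A, not shown) could bring recent resurfacing to light. Recording it would help interpretation, but under the present criteria the patient would still be eligible. Finally, the lack of a control is the larger limit on attribution in this proof-of-concept study, and an added exclusion does not change that. It is nonetheless no reason to leave an avoidable source open.

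**Conclusion.** The omission is real. The entry rule guards against recent neuromodulators and fillers and against blepharoplasty, but admits a recently resurfaced patient to an uncontrolled series read as change from the week-0 photograph. The conclusion rests on one assumption that the documents neither state nor rule out: that a recent resurfacing effect may still be evolving after week 0 and may affect the grade. The size and direction of the resulting bias are unknown, and it may be zero if no such patient is enrolled. Closing the gap is a cheap improvement, not the correction of a demonstrated error.

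**What to change.** In section 2, add resurfacing of the periocular skin (laser, energy-based or chemical peel) to the existing look-back exclusion. Use the 6-month window the protocol already applies to neuromodulators and fillers, or another period that the investigators justify; the documents do not establish a length specific to resurfacing. Attach the new item to the periocular region only, since the present wording also refers to the frontalis, a muscle. Add one question on earlier resurfacing and its date at the initial visit, and keep the answer with the baseline data. Leave the surgical exclusion as it is.

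The cost is one phrase in the exclusion criteria and one history question. The downside is that a few candidates, mainly from the cosmetic clinic, become ineligible or must wait.

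### Does the recruiting script's four months contradict the twelve-week schedule in a way that calls for a change to the plan?

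*Protocol*

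**What the plan says.** The protocol (Version 2) gives the length of participation in two sections.

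- **Section 2, Subject Population, recruiting script.** Faculty and residents approach candidates in the university's dermatology clinics. The script says that taking part involves "use of the product nightly as well as monthly visits for 4 months", and ends by asking whether the person would like to hear more.
- **Section 3, Procedure.** At the initial visit the study is discussed, written consent is obtained and application instructions are given. "An initial examination and photodocumentation will be performed" at that same visit. Patients then use the product nightly and "will be followed with Q 4 weeks appointments for a total of 4 visits".
- **Section 3, Data collection.** The schedule is repeated as four-weekly follow-up "for a total of 4 visits, 3 months of treatment". At the end, "each patient's photographs at weeks 0, 4, 8, and 12 will be graded by 2 blinded evaluators".

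Application instructions are gone over again at each visit, side effects are surveyed at follow-up visits, and there is an exit survey. The document schedules no visit, photograph or survey after week 12.

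**The concern.** The script says four months and the procedure says three. It looks as though the number of visits was turned into a number of months. In a single-arm study with no comparator, the length of nightly use is a large part of what defines the treatment, so two different lengths in one protocol deserve a check.

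Two consequences come to mind. A participant who took the script at its word might go on applying the product for about a month after the last photograph and side-effect survey. Alternatively, staff might hold the last visit at month 4, and the final graded photograph would then no longer be the week 12 one. Either would matter in a study of this size ("15 subjects will be recruited"), where the result rests on the change in dermatochalasis grade from week 0 to the later photographs.

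**Working it through.** **Inputs.** Section 3 gives a 4-week interval, 4 visits, 3 months of treatment and "photographs at weeks 0, 4, 8, and 12". The script in Section 2 gives nightly use, monthly visits and 4 months. The only outside convention is an average month of 365.25 / 12 = 30.44 days.

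**Step 1: reproduce the schedule in Section 3.** The baseline photographs are taken at the initial visit, so that visit is week 0 and the first of the four.

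- Span = (number of visits − 1) × interval = (4 − 1) × 4 = 12 weeks = 84 days.
- In calendar months: 84 / 30.44 = 2.8, which is 3 months in ordinary speech.
- Visit weeks: 0, 4, 8, 12, matching the list of graded photographs.

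The visit count, the stated duration and the photograph weeks therefore agree.

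**Step 2: take the script literally.**

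- 4 × 30.44 = 121.75 days, about 122 days or 17.4 weeks.
- Difference from Section 3: 121.75 − 84 = 37.75 days, about 38.
- Ratio: 121.75 / 84 = 1.45.
- Four-weekly visits from baseline within that span: weeks 0, 4, 8, 12 and 16, which is 5 visits.

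**Step 3: see whether some reading brings the two together.**

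| Reading of the script | Visits | Agrees with Section 3? |
|---|---|---|
| The months count the visits: one visit a month, four in all | 4 | Yes on visit count; the script then gives no separate length for nightly use |
| The months are the length of both nightly use and visits | 5 at four-week spacing, baseline included | No |
| Four follow-ups after a separate baseline (weeks 4, 8, 12, 16) | 4 plus baseline | No; the 3 months and the week 0 to 12 list rule it out |

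In the script's sentence the period sits next to the visits, so the first reading is natural, though not the only one. On the second the durations do conflict.

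**Step 4: see whether the feared consequences can occur together or follow from the text.** Thirty-eight unmonitored nights require the visits to stop at week 12. A fifth visit requires a visit at week 16, where the follow-up survey would apply. These are different scenarios and cannot be added together. Each also needs someone to act on the script rather than on Section 3:

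- For continued use, one sentence heard before consent would have to outweigh the consent discussion, the instructions at each visit and the exit survey.
- For a moved endpoint, staff at a single university under one principal investigator would have to schedule from a recruiting script and disregard a procedure section that gives the schedule three times in agreement.

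The 38 days are thus the gap between two phrases, not an estimate of exposure.

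**The case for a change.** The best case for acting is that the script is text spoken to candidates. It is there to standardise what several recruiters say, and on one ordinary reading it gives the wrong length of participation or else Section 3 does. The protocol names no date of last application, so the duration in Section 3 is the only other statement of when exposure ends. Section 4 (Risks) relies on side effects clearing once the product is stopped, and the last scheduled survey is at week 12. The edit would cost one line.

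Part of this stands. The wording is inconsistent, and the favourable reading settles the visit count without making every reading of the duration agree. The rest does not carry the weight put on it. The absence of a named last application is largely met by an explicit duration and a fixed last visit with an exit survey. What enrolled participants are told is a matter for the consent form, which is not among the pages shown, so no error there can be inferred. If the script is the text that is off, it overstates the commitment and conceals no burden. A cheap edit is worth making, but its low cost does not turn it into a flaw in the plan.

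**Conclusion.** The inconsistency is real and clerical. Section 3 gives one schedule in three mutually consistent ways, spanning 12 weeks, and that section governs treatment, visits, photographs and grading. The script in Section 2 is loosely worded and on its face up to about 38 days longer. The effect on planned exposure, assessment times, sample size and analysis is nil, because none of them is taken from the script.

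This rests on two assumptions: that staff run the study from the procedure section, and that the consent form (not shown) gives the same duration as that section. The sponsor can confirm the intended duration and bring the script and consent text into line at the next routine revision. That is editorial reconciliation and does not change the plan.
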